2.4 Data Collection and Analysis

Appointment 1/Baseline. Data will be collected on the participants first visit ("baseline") and will include the following: OSDI, visual acuity, slit lamp imaging, lissamine green staining, fluorescein, tear film break up time (TBUT), Schirmers 5 minute with anesthesia osmolarity, meibography, Keratograph5 redness evaluation, Lipiview lipid tear film thickness, , tear cytokine evaluation and impression cytology (for flow cytometry of labeled cells for inflammatory markers), and tear sample for ocular microbiome testing.

number identifier, and their data will be entered into an Excel Document ("data file") and RedCap database which will be kept on a secure server at Mayo Clinic Arizona.

[figure not shown]
At appointment 1, participants will receive the initial treatment of either MGX or MGX+IPL. At appointment 1, participants will be given Tobramycin-Dexamethasone ophth soln to use BID topically OU for 2 days, and told to avoid UV exposure for 3 weeks.

Appointment 2. 4-6 weeks after appointment 1, at appointment 2, participants will be evaluated using OSDI, visual acuity, Icare tonometry, slit lamp imaging, lissamine green staining, fluorescein staining. This data will be entered into the data file. Participants will receive their second treatment of either MGX or MGX+IPL. At appointment 2, participants will be given Tobramycin-Dexamethasone ophth soln BID for 2 days, and told to avoid UV exposure for 3 weeks

Appointment 3. 4-6 weeks after appointment 2, at appointment 3, participants will be evaluated using OSDI, visual acuity, Icare tonometry, slit lamp imaging, lissamine green staining, fluorescein staining. This data will be entered into the data file. Participants will receive their second treatment of either MGX or MGX+IPL. At appointment 3, participants will be given Tobramycin-Dexamethasone ophth soln BID for 2 days, and told to avoid UV exposure for 3 weeks

Appointment 4. 4-6 weeks after appointment 3, at appointment 4, participants will be evaluated with the following: OSDI, visual acuity, slit lamp imaging, lissamine green staining, fluorescein, tear film break up time (TBUT), Schirmers 5 minute with anesthesia osmolarity, meibography, Keratograph5 redness evaluation, Lipiview lipid tear film thickness, , tear cytokine evaluation and impression cytology (for flow cytometry of labeled cells for inflammatory markers), and tear sample for ocular microbiome testing. Participants will receive their final treatment of either MGX alone or MGX + IPL. At appointment 4, participants will be given Tobramycin-Dexamethasone ophth soln BID for 2 days, and told to avoid UV exposure for 3 weeks. (Data from Vegunta et al (2016) [19] proved that 3 treatments alone are sufficient to produce a symptomatic MGX/IPL response with improvement of dry eye symptoms and signs. We did not expect that subjects would be compliant to return for a 5th appointment if there was no treatment being performed at that visit.)

Data Analysis. After the completion of 4 treatments, and the collection of data as outlined above, data will be analyzed using statistical methods for changes to the aforementioned tests. The analysis will be conducted by a research trainee who will be blinded to the participant groups. That is, they will receive the identifiers "Group 1" vs "Group 2", without the identification of which group received MGX/IPL vs MGX alone.

ÌPL)

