1.4 Summary and Hypothesis

Given the aforementioned data and relative lack of prospective studies regarding the use of MGX/IPL in patients with DED, we propose a prospective, randomized, case-controlled clinical pilot study to examine the efficacy of IPL for both subjective and objective measures. 20 patients with DED will be recruited, and will be randomly assigned to one of two groups: MGX alone, or MGX with IPL, and will undergo treatment every 4-6 weeks for 4 total treatment. Subjectively, participants will be scored using dry eye symptom questionnaires, including the OSDI, prior to treatment and post-treatment. Objective measures at baseline and at the end of the study will include tear cytokine levels, impression cytology for inflammatory markers, meibography, tear osmolarity, and ocular microbiome testing (see Chapter 2).

We hypothesize that use of MGX with IPL will lead to greater improvement in subjective dry eye symptoms, improved objective meibomian gland measures, and an upregulation in tear cytokines such as TGF-B1 and downregulation of inflammatory markers, such as IL-10, and improvement of ocular microbiome load, as compared to participants treated with MGX alone.

Given the lack of adverse effects reported in the literature, we do not anticipate study participants will experience adverse effects with proper performance of the IPL and testing procedures. For IPL subjects, masking using IPL-aid for both eyes will be used to protect the ocular structures. After Fitzpatrick skin type assessment, test application of IPL will be performed at the right preauricular skin and evaluated for erythema or skin change prior to

proceeding with the rest of the IPL application. We will record all events and include them in our analyses.

Chapter 2: Study Overview and Design

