Meibography Keratograph. Meibography is a tool to measure the amount of meibomium gland atrophy (MGA). MGA has been reported to be an important cause of dry eye.[27, 28] Images are objectively measured using ImageJ (NIH) based on a previously published report. [29] Results are reported from 0-100% atrophy of total surface area. We hypothesize a significant improvement in MGA with MGX/IPL versus MGX alone. Cost for meibography is estimated at \$20 for each test and will be bundled into OPH EST LIMITED EXAM CPT (see 3.3 below).

Lipiview. Lipiview measures lipid tear film thickness by interferometry on Lipiview instrument. Results are reported on a scale from 20-100. We hypothesize a decrease in the absolute thickness of tear film lipid layer with MGX/IPL versus MGX alone. Cost for lipiview is estimated at \$20 for each test and will be bundled into OPH EST LIMITED EXAM CPT (see 3.3 below).

Tear Cytokine. Tears will be collected at baseline and after the third treatment to be analyzed for the following markers: IL-1B, IL-6, IL-8, IL-10, IL-17, IFNg, TNFa, and TGFB1. Tear cytokine analysis of these markers has previously been shown as a marker of ocular surface inflammation, and is upregulated in DED.[30-33] We hypothesize an increase in TGFB1 and a decrease in the aforementioned inflammatory cytokines with MGX/IPL versus MGX alone. Samples will be collected at baseline and frozen at -80*C until analyzed using a pre-made custom plate (Millipore, USA). For 40 samples (20 patients x 2 samples each (1 pre and 1 post treatment), we will require 1 96-well plate at the cost of \$1500 + \$260 service fees. Additionally, to analyze TGFB1, we will require a separate plate at the cost of \$500 + \$300 for all samples. Therefore, the final cost for tear cytokine analysis will be \$2,560 for all samples for the entirety of the study.

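### The final assessment estimates the effect of three treatments, not four, and no scheduled contact follows the fourth

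*Combined protocol and SAP*

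**What the plan says.** Section 1.4 states that patients "will undergo treatment every 4-6 weeks for 4 total treatment". It has symptoms scored before treatment and post-treatment, objective measures taken at baseline and at study end, and all events recorded.

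Section 2.4 sets out the visits. Baseline assessment and the first treatment share a visit: "At appointment 1, participants will receive the initial treatment of either MGX or MGX+IPL". The closing battery is described as follows: "4-6 weeks after appointment 3, at appointment 4, participants will be evaluated with the following: OSDI, visual acuity, slit lamp imaging", and the list continues through the signs and biomarkers. Only after that list does the text say: "Participants will receive their final treatment of either MGX alone or MGX + IPL". A note in the same paragraph cites the sponsor's own earlier chart review as showing that three treatments are enough to produce a response, and explains why there is no later visit: "We did not expect that subjects would be compliant to return for a 5th appointment" without a treatment being given. The analysis paragraph then opens: "After the completion of 4 treatments, and the collection of data as outlined above, data will be analyzed using statistical methods for changes".

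Section 3.2 gives the timing for tear cytokines explicitly: "Tears will be collected at baseline and after the third treatment to be analyzed for the following markers".

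**The concern.** The summary leads a reader to expect the effect of the full four-treatment course. The schedule delivers the effect of three treatments, and no sentence says so when describing the endpoint or the comparison. A report drafted from Section 1.4 could attach a three-treatment result to a four-treatment regimen.

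The second issue is safety observation. After each of the first three treatments the patient returns 4-6 weeks later. After the fourth, no visit, call or questionnaire is described, so the undertaking in Section 1.4 to record all events has no planned means of being met for the last exposure. Section 1.4 expects no adverse effects. But Section 1.2 cites a retrospective series of 91 records on the combined treatment in which 13% of patients had an adverse event, so that expectation is not secure enough to make follow-up unnecessary.

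**Working it through.** The documents give no alpha, power, effect size or standard deviation, so there is no statistical figure to reproduce. The check is a count of visits, treatments and samples.

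**Inputs**
- Treatments per patient: 4, spaced 4-6 weeks apart (Sections 1.4, 6.0, 7.0).
- Patients: 10 per arm, 20 in total (Section 2.3).
- Samples for tear cytokines: 40, one before and one after treatment per patient (Section 3.2).
- Vials: 640, at 8 per session (Section 3.2, pharmacy costs). Only the count is used here. The product named there differs from the drops named in Section 2.4, which is a separate point to reconcile.

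**The plan's own counts**
- Samples: 20 patients × 2 = 40. This agrees and implies one post-treatment sample each.
- Sessions: 640 / (20 patients × 8 vials) = 4 per patient. This agrees with four treatments.

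**Timeline**, with gap g between appointments and treatments at weeks 0, g, 2g and 3g:

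| Gap | Treatments at weeks | Final assessment | Treatments completed by then | Weeks since last completed treatment |
|---|---|---|---|---|
| 4 weeks | 0, 4, 8, 12 | week 12, before treatment 4 | 3 | 4 |
| 6 weeks | 0, 6, 12, 18 | week 18, before treatment 4 | 3 | 6 |

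Scheduled follow-up after treatment 4 is 0 weeks in either case.

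**Is the order within appointment 4 secure?** Section 2.4 lists assessment first and treatment second. Section 3.2 independently places the second tear sample after the third treatment. The note about a fifth appointment also makes sense only if the closing data are collected before the fourth treatment. Section 2.4 does call the appointment 3 treatment the second one; by count it is the third, which agrees with Section 3.2.

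**Which outcomes are affected?** Those listed at appointment 4: OSDI, visual acuity, slit lamp imaging, both stainings, TBUT, Schirmer, osmolarity, meibography, redness, lipid thickness, tear cytokines and impression cytology. The quality-of-life survey, tonometry and MMP9 are not in the appointment 4 list, so the point makes no claim about them. The microbiome is unclear. Section 2.4 lists a tear sample, Section 3.2 conjunctival swabs, and Sections 5.0, 6.0 and 7.0 gland material expressed during treatment. Expressed material at appointment 4 would come from the fourth session and, in the IPL arm, after the fourth IPL application. It still could not show a later response to that session.

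**Sessions with no scheduled follow-up**
- Both arms: 20 × 1 = 20 of 20 × 4 = 80, or 25%.
- IPL arm: 10 × 1 = 10 of 10 × 4 = 40, or 25%.

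**The case against.** The best defence is that nothing is hidden. The note in Section 2.4 stands directly before the analysis paragraph and says that three treatments are considered sufficient and why no fifth visit is planned. The sentence "After the completion of 4 treatments, and the collection of data as outlined above, data will be analyzed using statistical methods for changes" mainly says when the analysis is run and points back to the schedule, so it can be read as consistent with it. This stands. The sentence does not itself claim a four-treatment effect; the mismatch rests more on Section 1.4, whose wording is loose rather than contradictory. But disclosing a visit order does not define an endpoint, and no other text does so.

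A reader might infer that the comparison between arms is compromised. The documents do not support that: both arms follow the same schedule and are assessed at the same point, so the ordering introduces no bias. Nor do they support saying that every outcome precedes the fourth treatment, given the microbiome material and the measures missing from the appointment 4 list.

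A reader might also infer that events after the fourth treatment cannot be captured at all. That goes too far. Events during the session can be seen in clinic, and spontaneous reports are not excluded. What can be said is that no scheduled contact is described. Even this needs some caution, because a figure is missing from Section 2.4 and some of its text is broken.

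**Conclusion.** The point holds in limited form. For the outcomes listed at appointment 4, with the microbiome as a possible exception, the planned change from baseline estimates the effect 4-6 weeks after three treatments, and the documents never state the endpoint that way. Assessing there is a defensible choice that the sponsor explains; the defect is in how the endpoint is described, and no effect on the estimate, power or error rate is shown.

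The safety gap goes beyond wording. Followed as written, the plan has no scheduled way to observe events after the last of four exposures, for 20 of 20 patients. The 25% share describes unobserved exposure and is not a measure of lost efficacy information or of bias.

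The conclusion assumes that appointment 4 runs in the order listed, that all patients complete four sessions, and that no follow-up contact is specified in material missing from the text available.

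**What to change.** 1. In Sections 1.4 and 2.4, define the endpoint as change from baseline to appointment 4, after three treatments and before the fourth, and word all conclusions as a three-treatment effect. Correct the treatment count at appointment 3.
2. Reconcile the microbiome specimen (tear sample, conjunctival swab or expressed gland material) across Sections 2.4, 3.2, 5.0, 6.0 and 7.0, and state whether it is taken before or during the fourth session.
3. Add one remote contact by telephone, mail or portal 4-6 weeks after the fourth treatment, identical in both arms, covering adverse events and the OSDI. The OSDI has 12 questions with one-week recall and needs no examination, so this avoids the attendance problem that ruled out a fifth appointment.
4. Label that later OSDI secondary and descriptive. No sham IPL is described, so participants would probably know their arm, and a questionnaire cannot support a four-treatment claim for signs or biomarkers.

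The cost is some protocol wording, one short questionnaire for each of 20 patients and a narrower stated claim. Sample size and the treatment schedule do not change.

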2.5 Design Summary

Power calculation for sample size for biostatistician

Range listed for endpoints

- OSDI (range 2-100)
- QOL
- VA - Slit lamp
- Slit lar
 TA
- Fluorescein (0-15)
- Lissamine Green (0-6)
- Lipiview (20-100)
- Tear Osmolarity (280-320)
- Meibography (0-100)
- Redness (Keratograph5)
- TBUT (0-10)
- Tear cytokines
- Impression Cytology for inflammatory markers
- Ocular microbiome testing

Chapter 3: Experimental Procedures and Cost

3.1 Subjective Parameters

Ocular Surface Disease Index (OSDI). OSDI is the National Eye Institute Visual Functioning Questionnaire and has been proven to be valid and reliable instrument for assessing DED. A copy has been attached in Chapter 4. The range of results is 2-100. We hypothesize a decrease in OSDI levels with MGX/IPL versus MGX alone. Cost for OSDI is estimated at \$20 for each test and will be bundled into OPH EST LIMITED EXAM CPT (see 3.3 below). OSDI Survey is included in Chapter 4.1.

QOL Survey.

Cost for QOL is estimated at \$20 for each test and will be bundled into OPH EST LIMITED EXAM CPT (see 3.3 below). QOL Survey is included in Chapter 4.2.

3.2 Objective Parameters

Visual Acuity (VA). VA will be recorded in Snellen format for each eye as a safety measure. We hypothesize no changes to VA will be seen between groups. Cost for VA is estimated at \$20 for each test and will be bundled into OPH EST LIMITED EXAM CPT (see 3.3 below).

Applanation tonometry (TA). Recorded intraocular pressure (IOP) for each eye as measured by Goldmann applanation tonometry. IOP measurement and recording is a safety measure. We hypothesize no changes to IOP will be seen between groups. Cost for TA is estimated at \$20 for each test and will be bundled into OPH EST LIMITED EXAM CPT (see 3.3 below).

Conjunctival Injection Score (Redness). Analyzed using slit lamp images from Keratograph 5. Increased injection has been associated with increased DED symptoms. Score is graded as 0-3, with 0 being no conjunctival injection and 3 being marked injection. We hypothesize a decrease in conjunctival injection score with MGX/IPL versus MGX alone. Cost for conjunctival injection scoring is estimated at \$20 for each test and will be bundled into OPH EST LIMITED EXAM CPT (see 3.3 below).

Lissamine Green staining of the interpalpebral conjunctiva. Conjunctival staining is an effective tool to examine epithelial damage. It is easy to perform and has been proven with good reproducibility. We hypothesize an improvement in conjunctival staining with the use of MGX/IPL versus MGX alone. Two areas will be graded from 0-3 in severity. Cost for lissamine green staining is estimated at \$20 for each test and will be bundled into OPH EST LIMITED EXAM CPT (see 3.3 below).

Fluorescein Cornea Staining (FCS). Corneal staining is an effective tool to examine epithelial damage. It is easy to perform and has been proven with good reproducibility. We hypothesize an improvement in corneal staining with the use of MGX/IPL versus MGX alone. Five areas

each will be graded from 0-3 in severity. Cost for FCS is estimated at \$20 for each test and will be bundled into OPH EST LIMITED EXAM CPT (see 3.3 below).

MMP9. A reliable test used as a marker for inflammation which may provide evidence of ocular surface disease or dry eye with 85% sensitivity and 94% specificity.[21-23] Data has shown abnormal expression of MMP9 expression in DED, which is linked to increased efficacy with the use of anti-inflammatory agents such as cyclosporine or doxycycline.[21, 22] Therefore, this test is a valuable indication of inflammation in DED. Results of the test are reported as positive or negative. We hypothesize that patients treated with MGX/IPL versus MGX alone will show a decrease in MMP9 expression over the course of the trial. Cost for MMP9 testing is estimated at \$20 for each test and will be bundled into OPH EST LIMITED EXAM CPT (see 3.3 below).

Tear Break Up Time (TBUT). Considered a mechanism and contributor of DED symptoms [23]. Severe disease criteria cut off is generally considered <3seconds. Split second stopwatch is used with the aid of fluorescein dye. Data has shown TBUT is an DED and is frequently used as a screen for DED.[24] We hypothesize an increase in TBUT with MGX/IPL versus MGX alone. Cost for TBUT is estimated at \$20 for each test and will be bundled into OPH EST LIMITED EXAM CPT (see 3.3 below).

Schirmers. Schirmers test is used to evaluate aqueous tear production and therefore is used to aid in possible diagnosis of DED.[23, 25] Results are abnormal if there is <5mm of wetting after 5 minutes. We hypothesize an increase in Schirmer's testing with MGX/IPL versus MGX alone. Cost for Schirmers testing is estimated at \$20 for each test and will be bundled into OPH EST LIMITED EXAM CPT (see 3.3 below).

Tear Osmolarity. Studies have shown tear osmolarity to be an important contributor to DED, as it parallels disease severity and responds to treatments.[25, 26] It is, therefore, an accurate and reliable marker of inflammation. Tear osmolarity is evaluated on a continuum, with severe disease being reported as >315 mOsms/L.[26] We expect an improvement (decrease in absolute value) in measures of tear osmolarity with MGX/IPL versus MGX alone. Cost for tear osmolarity is estimated at \$20 for each test and will be bundled into OPH EST LIMITED EXAM CPT (see 3.3 below).

Meibography Keratograph. Meibography is a tool to measure the amount of meibomium gland atrophy (MGA). MGA has been reported to be an important cause of dry eye.[27, 28] Images are objectively measured using ImageJ (NIH) based on a previously published report. [29] Results are reported from 0-100% atrophy of total surface area. We hypothesize a significant improvement in MGA with MGX/IPL versus MGX alone. Cost for meibography is estimated at \$20 for each test and will be bundled into OPH EST LIMITED EXAM CPT (see 3.3 below).

Lipiview. Lipiview measures lipid tear film thickness by interferometry on Lipiview instrument. Results are reported on a scale from 20-100. We hypothesize a decrease in the absolute thickness of tear film lipid layer with MGX/IPL versus MGX alone. Cost for lipiview is estimated at \$20 for each test and will be bundled into OPH EST LIMITED EXAM CPT (see 3.3 below).

Tear Cytokine. Tears will be collected at baseline and after the third treatment to be analyzed for the following markers: IL-1B, IL-6, IL-8, IL-10, IL-17, IFNg, TNFa, and TGFB1. Tear cytokine analysis of these markers has previously been shown as a marker of ocular surface inflammation, and is upregulated in DED.[30-33] We hypothesize an increase in TGFB1 and a decrease in the aforementioned inflammatory cytokines with MGX/IPL versus MGX alone. Samples will be collected at baseline and frozen at -80*C until analyzed using a pre-made custom plate (Millipore, USA). For 40 samples (20 patients x 2 samples each (1 pre and 1 post treatment), we will require 1 96-well plate at the cost of \$1500 + \$260 service fees. Additionally, to analyze TGFB1, we will require a separate plate at the cost of \$500 + \$300 for all samples. Therefore, the final cost for tear cytokine analysis will be \$2,560 for all samples for the entirety of the study.

Impression Cytology. Impression cytology is used to sample conjunctival epithelium which has been shown to be affected in DED. [34, 35] The test is minimally invasive, and is well validated within the literature.[34, 35] Using flow cytometry, the expression of 4 markers: HLA-DR (an inflammatory marker), Fas antigen (CD95), Fas ligand, and APO2-7 (apoptotic markers), will be quantified based on previously published reports.[36] Published studies have shown these markers to be upregulated in DED and therefore a biomarker of ocular surface inflammation. [34, 37] Cost is estimated to be \$4,000 for all samples for the entirety of the study, which includes antibodies, consumables and service charges.

Microbiology Identification. This test is used to examine the changes in microbiological flora of the eye. Conjunctival swabs will be obtained from patients and sent for RNA sequencing. Previous studies have shown ocular surface bacteria to be related to various ocular surface disease.[38] Additionally, the presence of *Demodex* has been shown to influence meibomian gland dysfunction, cause inflammation, and lead to changes in tear cytokine levels such as IL-17[39, 40]. Through this method, we will be able to assess changes in the ocular microbiome, including alterations in *Demodex*, with MGX/IPL versus MGX alone. Cost is estimated to be \$30.07/sample, with a total cost for all 40 samples \$2,500. See Section 5 for detailed protocol.

Pharmacy costs: Acuvail costs total \$10,000. This is due to the need for 8 vials of the preservative free ampules to be given for OU BID dosing after each treatment session, totaling 640 vials.

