2.3 Participant Randomization

Once inclusion criteria have been met, patients will be randomized to one of two groups using a random number generator. 10 patients will be randomized to the control group, in which they will receive MGX every 4-6 weeks; and 10 patients will be randomized to the treatment group, in which they will receive MGX and IPL every 4-6 weeks. Biomarker and microbiome labs and data analyzer will be masked to treatment group.

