5.0 Ocular Microbiome Protocol (NAU [name]/[name] Lab)

Microbiome samples from meibomian gland expressed material were collected in the office under strict aseptic precautions in the ophthalmology clinic using sterile gloves and instrumentation. Material was collected and transferred to sterile swab for right eye and left eye samples (COPAN LQ Stuart Transport Swab, COPAN Italia S.p.A, Brescia, Italy). Any contaminated swabs were discarded and repeat sampling performed. After collection, the swab tips were cut with sterilized scissors and placed into Eppendorf tubes and placed in dry ice container. The samples were immediately sent for freezing frozen in a -90°C bath of Novec engineered fluid (3M HFE-7000) cooled in a HistoChill freezing bath (SP Scientific HC80A0). The time from the start of harvest to freezing was approximately 10 -15 minutes. No saline, embedding medium or preservative was added. Unique identification numbers were assigned to each individual container with bar code labels. Biospecimens were stored in ThermoFisher Ultra Low Temp upright freezers at -80°C until shipped to [name]/[name] lab at NAU on dry ice and then stored at -80°C until ready for analysis.

DNA Extraction

Total genomic DNA was extracted using the QIAamp DNA Mini Kit (Qiagen; 51304) with some prior modifications. Briefly, swab heads were placed in sterile 2mL microcentrifuge tubes with 400uL of lysis buffer (20mM Tris-HCI [pH 8.0], 2mM EDTA, 1.2% Triton X-100) containing 1mg/mL Lysozyme (Sigma-Aldrich; L7773), 30U/mL Lysostaphin (Sigma-Aldrich; L2898) and 375U/mL Mutanolysin (Sigma-Aldrich; M4782). Specimens were incubated at 37°C for 1 hour and both the lysates and the swabs were transferred to bead-beating tubes containing 373mg of 0.1mm-diameter zirconia/silica beads (Biospec; 11079101z). Bead-beating was performed at 2100 rpm for 1 min using a Digital Vortex Mixer (Fisher Scientific; 0215370) with a vortex adapter (Mo-Bio; 1300-V1-24). The samples were centrifuged at 12,000xg for 5 minutes and the supernatant was transferred to sterile 1.7mL microcentrifuge tubes. Then, 20uL Proteinase K (20mg/mL) and 400uL Buffer AL were added to each sample and incubated at 56°C for 30 minutes. Further DNA purification was performed as described by the manufacturer.

Library Preparation

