To determine the baseline variability of the bacterial microbiota within an individual, the V3-V4 region of the 16S rRNA gene was sequenced on the Illumina MiSeq. All analyses were performed on an operational taxonomic unit (OTU; number of clusters of similar sequences) table rarefied to 5500 sequences/sample. Alpha-diversity, which is used to assess diversity, evenness, and richness in a community in a single sample, was measured to ascertain differences in the microbiota between IM and MM across the spectrum of CRS disease. Alpha diversity indices studied were: Faith's phylogenetic diversity (measure of biodiversity incorporating phylogenetic difference between species) and Shannon diversity (richness and evenness; "evenness" is a measure of relative abundance of different species that make up the richness in that area)]. A permutational t-test (999 Monte Carlo permutations) was used to determine changes in alpha-diversity (diversity within a sample). Alpha diversity values were projected onto an image of the sinonasal cavity on the MM middle or IM using SitePainter²².

Beta diversity (comparison of samples to each other to measure the distance or dissimilarity between each sample pair) was performed using UniFrac distance matrices generated in QIIME 1.9.0. Average weighted and unweighted UniFrac values were calculated between subjects. Principal Coordinates Analysis (PCoA) plots were used for visualization of the data present in the beta diversity distance matrix using Emperor. Permutational analysis of variance (PERMANOVA) using the adonis function in the R Vegan package was used to determine significance in distance matrices across samples by metadata categories. Procrustes analysis was performed on the first three dimensions of a PCoA generated using a weighted UniFrac distance matrix and a Monte Carlo simulation was performed with 10000 permutations to determine significance. Procrustes sum of squares (m^2) and correlation [$r = \sqrt{(1 - m^2)}$] are reported. To confirm the Procrustes findings, a two-sided Mantel test with 10000 permutations was performed on weighted UniFrac distances matrices generated independently for each sample within a pair.

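### Section 5.0 describes a swab from each eye but states no patient term in its group tests; if eyes are counted separately, a 5% error rate becomes about 9% to 17%

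*Combined protocol and SAP*

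**What the plan says.** **Unit of randomisation.** Section 2.3: "patients will be randomized to one of two groups using a random number generator". It then fixes the numbers: "10 patients will be randomized to the control group" and "10 patients will be randomized to the treatment group". Sections 6.0 and 7.0 have the lids of both eyes expressed in either arm, and 6.0 runs the light treatment from one side of the face to the other. Both eyes of a patient are therefore always in the same arm.

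**What is recorded per eye.** Section 3.2 is explicit for visual acuity ("VA will be recorded in Snellen format for each eye as a safety measure") and for pressure ("Recorded intraocular pressure (IOP) for each eye as measured by Goldmann applanation tonometry"). No change is hypothesised for either. For redness, staining, TBUT, Schirmer, osmolarity, meibography and Lipiview, the documents do not say whether one eye, both eyes or an average is used.

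**Microbiome.** The opening of section 5.0 says: "Material was collected and transferred to sterile swab for right eye and left eye samples". Under Sequence and Statistical Analysis, alpha diversity is tested with a permutational t-test. For beta diversity, PERMANOVA "was used to determine significance in distance matrices across samples by metadata categories". Neither test is given a patient term, strata or a restricted permutation. The microbiome cost in 3.2 is for 40 samples.

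**Cytokines.** Section 3.2 counts "20 patients x 2 samples each (1 pre and 1 post treatment", which is one sample per patient per visit.

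**Clinical analysis.** Section 2.4 promises statistical methods applied to changes in the tests. It names no test, model or unit of analysis.

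**The concern.** When treatment is assigned to the patient and given to both eyes, each patient is a cluster of two. Two eyes of one person usually resemble each other, so 20 eyes per arm carry less information than 20 patients would. A test that shuffles or compares eyes freely understates the standard error of the arm difference and rejects too often.

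Section 5.0 is the only analysis written in any detail, and its two group tests work on samples. An analyst who has two swabs per patient and follows that text would enter them as separate observations. For the clinical signs, section 2.4 has the analysis done by a trainee who is given only group labels. Nothing there tells that trainee whether 20 patients or 40 eyes should be entered.

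**Working it through.** **Inputs from the documents.** 10 patients per arm (2.3); both eyes in the same arm (6.0, 7.0); two eyes per patient, so 20 eyes per arm.

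**Inputs assumed.** The documents state no significance level, sidedness or inter-eye correlation. I take a two-sided 5% level and let the correlation ρ run from 0 to 1. The plan has no figure of its own to reproduce here.

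**Formula.** With two eyes per patient the design effect is 1 + ρ, and the effective number per arm is 20/(1 + ρ). If eyes are treated as independent, the true error rate is approximately 2 × [1 − Φ(1.960/√(1 + ρ))]. For ρ = 0.5: 1.960/√1.5 = 1.600, which gives 11.0%.

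**Checks by simulation under no treatment effect.** A two-sample t-test on 20 against 20 eyes (200,000 runs per ρ), and a 999-permutation test that shuffles eyes freely (4,000 runs per ρ):

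| ρ (assumed) | Effective n per arm | Formula | t-test on eyes | Free permutation of eyes |
|---|---|---|---|---|
| 0 | 20.0 | 5.0% | 5.0% | 4.6% |
| 0.2 | 16.7 | 7.4% | 7.5% | not run |
| 0.3 | 15.4 | 8.6% | 8.6% | 9.1% |
| 0.4 | 14.3 | 9.8% | 10.1% | not run |
| 0.5 | 13.3 | 11.0% | 11.3% | 11.2% |
| 0.8 | 11.1 | 14.4% | 15.5% | 15.9% |
| 0.9 | 10.5 | 15.5% | 16.7% | not run |
| 1.0 | 10.0 | 16.6% | 18.2% | not run |

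The permutation column carries a Monte Carlo error of about half a percentage point (at 11.2%: √(0.112 × 0.888/4,000) = 0.005). PERMANOVA on distance matrices was not simulated; the permutation column is for a difference in means.

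**Where the rate doubles.** Setting the formula to 10% gives ρ = (1.960/1.645)² − 1 = 0.42. In the simulated t-test the crossing is near 0.40.

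**After the fix.** With the mean of the two eyes as one value per patient (10 against 10), the simulated error rate stays between 4.9% and 5.1% at every ρ.

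**Sample count.** 3.2 gives $30.07 per sample, 40 samples and a total of $2,500.
- $30.07 × 40 = $1,202.80.
- $30.07 × 80 = $2,405.60.
- $2,500/$30.07 = 83.1 samples.

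The count of 40 matches 20 patients × 2 time points. A count of 80 would match 20 × 2 time points × 2 eyes. It would also match 20 patients × 4 treatments with one sample each, because 6.0 and 7.0 send expressed material for testing without limiting this to the first and last visits. The price alone does not settle which is meant.

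**The case against.** **Section 5.0 never says that eyes are independent.** A reader might infer that it does. The lack of a patient term is silence, and the same section averages UniFrac values between subjects and uses paired Procrustes and Mantel procedures. That is fair, and it limits the claim to what is not stated. But the averages are descriptive, and Procrustes and Mantel measure agreement between paired samples. Neither supplies a patient term for the t-test or PERMANOVA.

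**The text was evidently written for another study.** It is in the past tense and refers to sinonasal sites, so it is weak evidence of how these two arms will be compared. That stands. It also means that no microbiome analysis suited to this trial is written down.

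**The budget counts 40 samples.** If eyes are pooled into one sample per patient per time point, a between-arm test at one visit has no two-eye problem. This stands as a possible reading, but it sits beside a per-eye collection procedure and a price that fits about 80.

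**The explicit per-eye clinical measures are safety measures.** A reader might infer that all the ocular signs are collected and analysed per eye. The documents support that for acuity and pressure only. The staining ranges in 2.5 (2 areas × 3 = 6; 5 areas × 3 = 15) are single-eye scores, which fit one study eye, an average or two separate eyes equally well. For these signs the gap is that the eye is not specified.

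**Repeat visits.** A reader might also infer that treating visits as separate subjects inflates the error rate. This is not shown. In a before-and-after contrast, ignoring positive within-patient correlation makes standard errors too large, and no section plans to pool visits in a between-arm test.

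**Conclusion.** The point holds in a conditional form. Patients are the randomised unit, section 5.0 describes a swab from each eye, and its two group tests state no patient term. If both eyes enter as independent samples, the two-sided 5% error rate for 10 against 10 patients becomes about 9% to 17% for inter-eye correlations of 0.3 to 0.9. It is tempting to say flatly that the rate would more than double. The documents do not support that, because doubling needs a correlation above about 0.4 and none is given, for levels or for changes.

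The result rests on the assumed 5% level, the assumed correlations and two swabs per patient at the visit compared. For clinical signs the finding is weaker: the eye and the unit of analysis are unspecified, so inflation is a risk and not a stated method. OSDI and quality of life are patient-level, and cytokines are counted once per patient per visit, so none of these is affected.

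**What to change.** **Section 5.0.** Use one value per patient per visit, by pooling or averaging the two eyes. Alternatively keep both swabs and permute arm labels by whole patient in the permutational t-test and in PERMANOVA. Permuting within patients would not serve, because the arm does not vary within a patient.

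**Section 3.2.** Reconcile the 40-sample count, the unit price and the total with the right-eye and left-eye collection in 5.0, and state the number of swabs per patient per time point.

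**Section 2.4.** State that the patient is the unit of analysis for any sign measured in both eyes, using the mean of the two eyes or a mixed model with a patient random effect. Say for each sign which eye or eyes are measured.

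**Cost.** A few sentences and no new data. Confidence intervals will be wider than if eyes were counted separately, which reflects the information that 10 patients per arm can give.
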